Phase 1 (n=100): Phase 1 initiates where the prior pragmatic clinical trial (NCT053339750, IRB 21-011596) concluded. This phase of the study will advance the technology in material ways through shifting day 3 (patch removal) and day 5 (final photographic documentation of test site) to the participant in the study. Participants will be guided in the use of the application and primary iOS/iPhone photographic documentation; the study team will provide additional photographic documentation and review of the test site to establish the reference criterion.

Phase 2 (n=25): For phase 2, the patch will be placed on the inside of the arm by the participant. The study documentation will proceed identical to Phase 1.

Quality Checkpoint Decision: Patch able to be successfully applied by patient in >90% of the cases (fewer than 3 placement errors).

Phase 3 (n=25): In phase 3, the entire study will be patient-led, although on-campus visits will be required to obtain the allergen panel and evaluate the reference criterion. This phase will use a prototype novel test kit with printed instructions and necessary supplies to clean the arm, assemble the patch application jig, install the app, and perform the patch testing. Human observation and patient surveys will be conducted to evaluate the human factors aspects of the test kit.

For both Phases 2 and 3, participants will be invited to complete the Patient Journey questionnaire at least a week ahead of the scheduled visit 1 appointment by email. Responses will be summarized to suggest allergens that would be recommended based on past exposures. The recommendations will be constrained to only the set of allergens tested in this protocol (See Section 5.2). Participant will have the option to select the standard allergens used in Phase 1 of the study or use up to 10 of the recommended allergens based on the Patient Journey.

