5.2. Investigational allergens

5.2.1. Primary Test Site (arm 1)

The following ten allergens manufactured by AllergEAZE will be used for patch testing during the study. Potential adverse reactions include pruritus, irritation, skin discoloration, erythema, induration, blistering and ulceration. Pruritus can be managed over-the-counter antihistamines.

While most reactions self-resolve, more severe skin reactions would be managed with topical steroids.

1. Nickel sulfate hexahydrate, 2.5% (18.3%)
2. M. Pereirae resin, 25% / Balsam of Peru (9.2%)
3. Neomycin sulfate, 20% (7.8%)
4. Fragrance mix, 8% (6.7%)
5. Bacitracin, 20% (6.4%)
6. Carba mix, 3% (5.8%)
7. Quaternium-15, 1% (4.4%)
8. Benzoic acid, 5% (3.7%)
9. Propolis, 10% (3.5%)
10. Thiuram mix, 1% (2.8%)

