5.2.2. Secondary Test Site (arm 2)

As part of the technology development program, two secondary tests will be used. Each participant will be randomized to one of these two patches.

Combination Patch #1: Standard Panel Array of 10 Allergens Combined into 4 Wells

- 1: Metals: Nickel sulfate hexahydrate
- 2: Fragrance & Taste Enhancers: M. Pereirae resin, 25% / Balsam of Peru + Fragrance mix + Quaternium-15
- 3: Topical/Homeopathic: Neomycin sulfate + Bacitracin + Propolis
- 4: Fungicides: carba mix + Thiuram mix + Benzoic acid

Combination Patch #2: Common Jewelry & Cosmetic Patch

- 1: Common metal allergy: Nickel sulfate hexahydrate
- 2: Cosmetics: M. Pereirae resin, 25% / Balsam of Peru
- 3: Cleaners: Methylchloroisothiazolinone / methylisothiazolinolone
- 4: Fragrance: Fragrance mix

Combination Patch #3: Patient Identified Allergen Profiles

For Phase II and III of the study, the following ten allergens will be added to the pool of 10 unique allergens tested in the primary patch and the combination of allergens offered as a part of the two combination patches.

- Linalool
- P-phenylenediamine
- Benzisothiazolinone, 0.1p
- Methylchloroisothiazolinone / methylisothiazolinone
- Paraben mix
- Formaldehyde
- Tea Tree Oil
- Cobalt Chloride
- Disperse Dye (Blue Mix)
- Gold Sodium Thiosulfate

This patient-driven combination of allergens can have between 1 and 10 individual test sites allowing for measurement of preference for “body burden” and patch test configurations.

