5.3. Method for Assigning Allergens to Test Site Regions

To minimize complexity of the randomization process and preparation of the patch test for the primary test site, a total of four randomized placement sequences will be generated. Participants will be assigned to these sequences in consecutive order. This same randomization sequence will be used to randomize the secondary patch option to the participants with participants holding an odd study number receiving Combination #1 and even study numbers receiving #2. Note these two patches are largely identical except for how the allergens are combined with the exception that Combination #2 has methylchloroisothiazolinone / methylisothiazolinone added to it.

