There is a block of standard measures of diagnostic performance (e.g., sensitivity, specificity). These statistics will be computed as is customary for similar studies. The calculations will be performed two ways when possible. First, each test site will be assumed to be statistically independent in the rating. For the neural network, this is how the algorithm functions. For the human reading, there may be some correlation among the ratings based on the reactions, if any, that are observed. To address this, an exploratory analysis will be conducted using generalized estimating equations to examine the impact empirically the intercorrelations may have on the estimated precision of the estimates (i.e., confidence interval width).

Safety data will be summarized by tabulating adverse events for the study. These will be categorized according to allergen related or study protocol related.

The secondary test sites include allergens, in novel combinations, that were tested in the primary test site. A secondary analysis will be conducted to quantify the agreement of reactions to the same allergens alone (primary test patch) and in combination (secondary test patch). Kappa will be used to quantify this agreement.

Finally, participant feedback on the study including the wearability of the patch on the forearm will be summarized using standard qualitative methods. This will include the extraction of key themes as well as listing open ended feedback provided to the study team by the participants.

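### Combination #2 contains no combined wells, so the alone-versus-combination kappa needs to be restricted to the three mixed wells of Combination #1

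*Combined protocol and SAP*

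**What the plan says.** Section 7.2.2 starts from a premise about the secondary patch: "The secondary test sites include allergens, in novel combinations, that were tested in the primary test site". On that basis it plans to "quantify the agreement of reactions to the same allergens alone (primary test patch) and in combination (secondary test patch", and adds that "Kappa will be used to quantify this agreement". It does not state the unit of analysis, the eligible wells, how a well holding three allergens is matched to three single wells, or how the interval is computed.

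The comparator is the ten-item primary patch in 5.2.1 ("The following ten allergens manufactured by AllergEAZE will be used for patch testing during the study"). MCI/MI is not on it.

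Section 5.2.2 defines the two randomised secondary patches:

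- "Combination Patch #1: Standard Panel Array of 10 Allergens Combined into 4 Wells": well 1 is nickel alone, and wells 2, 3 and 4 each hold three primary-panel allergens.
- "Combination Patch #2: Common Jewelry & Cosmetic Patch": nickel, Balsam of Peru, MCI/MI and fragrance mix, one item per well.

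Section 5.3 gives #1 to odd and #2 to even study numbers and says: "Note these two patches are largely identical except for how the allergens are combined". The same sentence goes on to disclose that #2 adds MCI/MI.

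For Phases 2 and 3, section 3.1 says: "Participant will have the option to select the standard allergens used in Phase 1 of the study". The alternative is up to ten allergens recommended from the questionnaire.

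**The concern.** The premise in 7.2.2 does not fit Combination #2 as 5.2.2 lists it. None of its wells mixes primary-panel allergens, so it cannot show whether mixing changes a reaction. Three of its wells, and the nickel well of Combination #1, put the same single item on both arms. Their agreement measures repeatability.

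Section 2.2 lists exploring allergen combinations that reduce the testing burden as a secondary objective, and this kappa is the only analysis described for it. If repeats and mixed wells go into one coefficient, good repeatability could cover a loss of detection in the mixed wells, which is the result the objective needs to see. If the eligible wells are left open, the choice could also be made after the data are seen.

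**Working it through.** The documents give no target, power or precision for this kappa, so there is no stated figure to reproduce.

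**1. Contents of the wells (5.2.1 and 5.2.2)**

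| | Combined wells | Single-item repeats | No Phase 1 comparator |
|---|---|---|---|
| Combination #1 | 3 (wells 2, 3, 4) | 1 (nickel) | 0 |
| Combination #2 | 0 | 3 (nickel, Balsam of Peru, fragrance mix) | 1 (MCI/MI) |

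Combination #1 holds 1 + 3 + 3 + 3 = 10 allergens, matching the primary panel. Combination #2 shares three of those ten, omits seven (neomycin, bacitracin, carba mix, quaternium-15, benzoic acid, propolis, thiuram mix) and adds one. Fragrance mix is counted as a single item because it occupies one well on both patches.

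**2. Phase 1 counts.** With n = 100 (3.1), odd/even allocation, and every participant wearing a secondary patch:

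- combined: 50 × 3 = 150
- repeats: 50 × 1 + 50 × 3 = 200
- no comparator: 50 × 1 = 50
- repeats among comparable well pairs: 200 / (200 + 150) = 57%

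If all 150 adaptive participants had the standard panel, the share would be the same: 300 / 525 = 57%.

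By allergen pair, each pair of participants (one per patch) gives 4 repeats and 9 allergens tested in a mixture, so repeats are 4 / 13 = 31%.

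**3. By expected positives.** Assume the bracketed percentages in 5.2.1 are positivity rates; the document does not label them. Per pair of participants, the repeat wells give 2 × 0.183 + 0.092 + 0.067 = 0.525. Under independence, a mixed well is positive with probability 1 − Π(1 − p): 0.190, 0.167 and 0.118 for wells 2, 3 and 4, sum 0.476. The repeat share is 0.525 / 1.001 = 52%. It is 51% if reactions within a well never overlap (sum 0.503) and 70% if they overlap fully (0.092 + 0.078 + 0.058 = 0.228).

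**4. Illustration of pooling.** Further assumptions, none from the documents: the primary patch is taken as the reference, a repeat well has sensitivity 90%, a mixed well detects 50% of wells with any positive constituent, and specificity is 98% throughout. Expected Phase 1 positives are 50 × 0.476 = 23.8 combined and 100 × 0.183 + 50 × 0.092 + 50 × 0.067 = 26.25 repeat. Kappa = (po − pe) / (1 − pe).

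| | Both + | Primary + only | Secondary + only | Both − | po | pe | Kappa |
|---|---|---|---|---|---|---|---|
| Combined | 11.89 | 11.89 | 2.52 | 123.70 | 0.904 | 0.776 | 0.57 |
| Repeats | 23.63 | 2.62 | 3.48 | 170.28 | 0.970 | 0.769 | 0.87 |
| Pooled | 35.51 | 14.51 | 6.00 | 293.97 | 0.941 | 0.772 | 0.74 |

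Sensitivity of the illustration, same formula:

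| Repeat sensitivity | Specificity | Mixed-well detection | Combined | Repeats | Pooled |
|---|---|---|---|---|---|
| 90% | 98% | 40% | 0.48 | 0.87 | 0.71 |
| 90% | 98% | 70% | 0.74 | 0.87 | 0.81 |
| 70% | 95% | 50% | 0.50 | 0.64 | 0.58 |
| 70% | 98% | 70% | 0.74 | 0.73 | 0.73 |

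In the last row a mixed well detects as well as a repeat well, so there is nothing for pooling to hide.

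**5. Precision after restriction.** SE = √(po(1 − po)/n) / (1 − pe), with mean prevalence 0.476 / 3 = 0.159. For n = 150 and an assumed kappa of 0.4, po = 0.840 and pe = 0.733, so the half-width is 1.96 × 0.112 = 0.22. At kappa 0.8 it is 0.14. For n = 225 (75 × 3, all on the standard panel) the range is 0.18 to 0.11. None of these allows for clustering.

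**The case against.** The strongest reply is that 7.2.2 never says all secondary wells will be pooled. It speaks of the same allergens alone and in combination. Read strictly, that already leaves out single-item wells and MCI/MI, and only Combination #1 wells 2 to 4 remain. This is a fair reading and the text does not exclude it. Two gaps survive it: the plan does not say so, and it gives no rule for matching one mixed well to three single wells. Half the participants would still contribute nothing to the question, and the purpose of Combination #2 would be unstated.

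Several stronger readings are tempting but go beyond the documents:

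- A reader might infer that the kappa will mostly measure repeat testing. That holds by well (57%) but not by allergen pair (31%), and the unit is not defined.
- A reader might infer that pooling would certainly mask a loss of detection. That depends on single-allergen repeatability, on which the documents give no figure.
- A reader might infer that Phase 2 and 3 participants lose their single-allergen comparators. Section 3.1 does not say which arm the choice applies to, and 5.2.2 lists the patient-selected panel under the secondary site. MCI/MI also joins the selectable pool in those phases, so some participants could have a comparator for it.
- A reader might infer that 5.3 is the passage in error. The list in 5.2.2 could equally be wrong.

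The stakes are limited. The objective is exploratory, this kappa is not among the endpoints listed in 7.2.2, and no hypothesis or threshold depends on it. The primary endpoint and sample size are unaffected.

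**Conclusion.** The mismatch is real. As listed in 5.2.2, Combination #2 has no combined wells, three single-allergen repeats and one well absent from the Phase 1 primary patch. That conflicts with the premise in 7.2.2 and with the description in 5.3. Half the participants therefore add no information on alone versus combination.

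Unless the kappa is restricted, 57% of comparable Phase 1 well pairs are repeats (31% by allergen pair), and pooling could hide poor agreement in the mixed wells. The counts rest on the 5.2.2 lists, equal allocation and every participant wearing the secondary patch; footnote c of the Schedule of Events calls the secondary sites optional. The kappas of 0.57, 0.87 and 0.74 illustrate a mechanism under assumed performance and do not predict the trial's result. This should be settled before analysis, but it does not threaten the trial's main conclusion.

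**What to change.** In 7.2.2:

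- Restrict the alone-versus-combination kappa to Combination #1 wells 2 to 4, in participants whose primary patch carries the constituent allergens.
- Make the well the unit. Count the comparator as positive if any of the well's three allergens is positive on the primary patch.
- Give a 95% confidence interval that allows for clustering of wells within participant, for example by resampling participants.
- Report the single-allergen wells (#1 well 1; #2 wells 1, 2 and 4) separately as a repeatability kappa.
- Leave out MCI/MI wells that have no primary comparator.

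Reconcile 5.2.2, 5.3 and 7.2.2 on what Combination #2 contains and what it is for, and state in 3.1 which arm the Phase 2 and 3 panel choice applies to.

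This is a change of wording and needs no new data. The cost is precision: the combination kappa would rest on about 150 Phase 1 wells, of which about 24 are expected to be positive under independence (about 11 with full overlap, 25 with none). Its half-width would be about 0.14 to 0.22 before clustering. That is the information the design holds on this question.

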2.2. Secondary Objectives

- To test if human review of photographs of skin patch tests are concordant with in person examination results.
- To demonstrate performance of DermAI application usage by the participant.
- To develop a database on novel photography modalities and explore performance advantages full spectrum photography and photogrammetry may bring to detecting contact dermatitis reactions.
- To explore novel combinations of allergens to lessen the burden of testing.
- To refine and optimize the lighting characteristics for photographing with visible spectrum and full spectrum lighting.

3. Study Design

[figure not shown]

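### Kappa alone, with no pairing unit stated, cannot show whether the mixed wells of Combination #1 keep the reactions seen to their components

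*Combined protocol and SAP*

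**What the plan says.** Section 2.2 lists as a secondary objective "To explore novel combinations of allergens to lessen the burden of testing". Section 5.2.2 describes Combination #1 as "Standard Panel Array of 10 Allergens Combined into 4 Wells". Its first well holds nickel only. The other three are mixtures of three:

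- Well 2: "M. Pereirae resin, 25% / Balsam of Peru + Fragrance mix + Quaternium-15"
- Well 3: "Neomycin sulfate + Bacitracin + Propolis"
- Well 4: "carba mix + Thiuram mix + Benzoic acid"

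All nine components are also tested singly on the primary patch (section 5.2.1). Under section 5.3, odd study numbers receive Combination #1 and even numbers Combination #2, which lists one item per well.

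The analysis, in section 7.2.2, is to "quantify the agreement of reactions to the same allergens alone (primary test patch) and in combination (secondary test patch", and the method is one sentence: "Kappa will be used to quantify this agreement". It gives no unit of pairing, no rule for matching one mixed-well result to three single results, no grade cut-off and no companion measure. The sensitivity and specificity paragraph in the same section discusses the neural network and the human readings, not the mixtures.

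**The concern.** Combining allergens lessens the burden of testing usefully only if the combined well still shows the reactions that the separate wells would have shown. That question has a direction: reactions lost by combining are a different failure from positives added by combining. Kappa treats the two alike. In addition, because the match is three to one, its value depends heavily on a pairing choice left to the analyst. The literal reading, same allergen alone and in combination, pairs each component with its well. It then scores a faithful mixture as disagreeing with every component that did not itself react.

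**Working it through.** The plan states no expected kappa, sample size or precision for this analysis, so there is no figure to reproduce.

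**Inputs.** Bracketed percentages from section 5.2.1, read as reaction rates (an assumption, since they are unlabelled). Their mean over the ten allergens is 6.9%, close to the 6.4% (132/2,060) reported for the prior trial in section 1.3.2. Reactions are taken as independent between allergens. A perfect mixture is one that is positive if and only if at least one component is positive alone. Nickel is left out because its well is not a mixture.

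**Probability that any component is positive.**
- Well 2: 1 − 0.908 × 0.933 × 0.956 = 0.190
- Well 3: 1 − 0.922 × 0.936 × 0.965 = 0.167
- Well 4: 1 − 0.942 × 0.972 × 0.963 = 0.118
- Mean 0.1585. The mean of the nine single rates is 0.0559.

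**Formula.** Kappa = (po − pe)/(1 − pe), where po is observed agreement and pe is the agreement expected from the margins.

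**A. Paired by allergen, perfect mixture.** Both positive 0.0559; alone only 0; mixture only 0.1585 − 0.0559 = 0.1026; neither 0.8415. Then po = 0.8974, pe = 0.0559 × 0.1585 + 0.9441 × 0.8415 = 0.8033, and kappa = 0.0941/0.1967 = 0.48.

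**B. Paired by well.**
- Perfect mixture: no discordant wells, kappa 1.00.
- One quarter of positive wells lost, none added: po = 0.9604, pe = 0.7603, kappa = 0.83.
- Half lost, none added: both positive 0.0793, alone only 0.0793, neither 0.8415. Then po = 0.9207, pe = 0.1585 × 0.0793 + 0.8415 × 0.9207 = 0.7873, and kappa = 0.1334/0.2127 = 0.63.
- None lost, 15.85% of component-negative wells positive in the mixture: added positives 0.8415 × 0.1585 = 0.133 of all wells, about 13 per 100. Then po = 0.8666, pe = 0.6421, and kappa = 0.2245/0.3579 = 0.63.

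The last two cases retain 50% and 100% of the reactions and have the same kappa.

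**Sensitivity to the assumptions.**

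| Setting | A: perfect, by allergen | B: half lost, by well |
|---|---|---|
| Section 5.2.1 rates, independent | 0.48 | 0.63 |
| Uniform 6.4% per site | 0.475 | 0.62 |
| Uniform 15% per site (section 7.1) | 0.44 | 0.55 |
| Within-person latent correlation 0.1 to 0.5 | 0.49 to 0.56 | 0.63 |

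Pooling the nickel well with the mixtures raises A to 0.55. It raises B to 0.75 if nickel is kept intact while the mixtures lose half, so pooling can hide the loss.

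**Information available.** About half of the 100 Phase 1 participants receive Combination #1. That gives 50 × 3 × 0.1585 = 23.8 component-positive mixed wells, or 150 × (1 − 0.85³) = 57.9 at the 15% planning rate. In the half-loss case, simulated kappas for 50 participants ran from about 0.42 to 0.80 (central 95%).

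**The case against.** The strongest reply is that the 0.48 follows from a pairing rule the plan never states. Paired by well, kappa behaves sensibly: 1.00, 0.83 and 0.63 as nothing, a quarter and a half are lost. One sentence fixing the unit would cure that part without dropping kappa. This stands. A reader might set 0.48 beside 0.63 and infer that kappa is simply the wrong measure, or that it ranks a perfect mixture below one that misses half. The documents do not support that, because the two values come from different pairings. Within the allergen pairing, a half-loss mixture has po = 0.9207, pe = 0.8737 and kappa 0.37, which is below 0.48.

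A reader might also attach verbal grades such as moderate or substantial agreement to these values. The plan sets no such label, threshold or decision rule, so no harm can be argued from one.

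It is also fair to say that the stated aim is agreement, for which a symmetric index is legitimate, and that the objective is exploratory and does not define success as reactions retained. That lowers the importance of the point. It does not make kappa sufficient, because 0.63 fits either half of the reactions lost or none lost. The retained and added shares come from the same two-by-two table, but the plan does not commit to reporting them or to the unit that defines the table.

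Finally, the two tests are on different arms, so not every discordant well is an effect of mixing. This also stands, and the fix allows for it.

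**Conclusion.** The point holds in this form: kappa alone, with the unit undefined, does not answer the question about combined wells. By allergen, a perfect mixture is held to about 0.48 (0.44 to 0.56). By well, kappa is valid as an agreement index, but about 0.63 (0.55 at a 15% site rate) can mean either half of the positive wells lost or none lost with added positives; at the section 5.2.1 rates the additions that match are about 13 per 100 wells. The figures rest on reading the section 5.2.1 percentages as reaction rates and on independence between allergens, with the ranges shown.

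The scope is narrow: three wells of one of the two randomised secondary patches. Matching is one to one in the nickel well of Combination #1 and in the wells of Combination #2 that repeat a primary-panel allergen. The analysis carries no hypothesis or sample size, and the primary endpoint is not affected. It is worth correcting because the correction is cheap and the present wording leaves a consequential choice to the analyst.

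**What to change.** In section 7.2.2, for the three mixed wells of Combination #1:

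1. State that the well is the unit, and that the single-allergen comparator is positive if any of its three component sites on the primary patch is positive at Day 5.
2. Apply one stated grade cut-off on both arms, for example the grade 1+ versus 0 split of section 7.2.1. Say how irritant readings (section 6.6) are counted; doubtful readings are grade 1, so that split would count them as positive.
3. Report (i) the share of component-positive wells that are also positive in the mixture, and (ii) the share of component-negative wells that are positive in the mixture, each with a participant-clustered 95% CI.
4. Report single-allergen wells such as nickel separately, as a benchmark for ordinary between-arm disagreement, and do not pool them with the mixtures.
5. Keep well-level kappa as a supplement.

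The cost is SAP wording; no new data are needed. The drawback is a wide interval for (i). With 24 positive wells and a share near 50%, the half-width is about 1.96 × √(0.25/24) = 20 percentage points before clustering; with 58 wells it is about 13 points. These counts cover Phase 1 only, since section 5.2.2 leaves it unclear how far Combination #1 is used in Phases 2 and 3.
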